### 10.2.5 Laboratory safety

A standard laboratory blood test will be performed at the screening visit (Visit1), on Day 14 (Visit 4), and End of treatment visit Day 28 (Visit 5) also performed in case of Early termination between Visit 2 and Visit 5. Routine serum hematology and chemistry samples will be collected in EDTA tubes and according to the study flow chart. They will be kept at the local

---

laboratory as per laboratory requirements and outlined in the investigator manual which will be available at each investigational site.

The standard laboratory blood test comprises:

- haematology: complete blood count (CBC) including haematocrit, haemoglobin, red blood cell count, white blood cell count with differential count and platelets,
- Serum chemistry including: sodium, potassium, chloride, calcium, phosphorous, urea, creatinine, creatinine clearance (calculated with the Cockcroft-Gault formula for patients <65 years old and CKD-EPI creatinine equation or with MDRD equation for patients ≥65 years old), uric acid, total protein, albumin, lactate dehydrogenase (LDH), Alanine Aminotransferase (ALT), Aspartate Transaminase (ASAT), alkaline phosphatase, GGT and total bilirubin, fasting glycaemia (fasting is not required at baseline), creatine phosphokinase (CPK), triglycerides, cholesterol.
- Glucose (no fasting is needed at screening)
- C Reactive Protein (CRP).
- A urine or blood pregnancy test (in females of childbearing potential) will be performed at the screening visit, on D14 (Visit 4), end of treatment visit (D28 visit 5) and end of study visit (D 84 Visit 6). A subject cannot be included with a positive urine test. Blood sample will be taken for confirmation of the pregnancy status at baseline and end of study visit. In case of positive results, the pregnancy outcome should be reported. For practicability, urine samples may be replaced by blood samples.

No centralized laboratory procedure for laboratory safety is planned. Only local laboratories will be used.

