### **11.1.3 Visit 3 (Day 7 ±2)**

The following tests and procedures will be performed:

- Checking for concomitant medication
- Inquiring about adverse event and fill an adverse event form if any
- Checking the patient's diary for tinnitus
- The investigator or designee will check the IP and oral corticosteroids diary for compliance.
- Vital signs: blood pressure and heart rate, temperature
- 12-lead digitalized ECG
- Otologic examination and tympanometry
- Audiometric tests: Pure tone audiometry, OAE tests (optional)
- Word and speech recognition Tests

The patient will be asked to complete specific questionnaires:

- Tinnitus and Vertigo presence and Severity (NRS)
- QoL: EQ-5D-5L;
- Tinnitus functional Index (TFI)
- C-SSRS

The patient will be asked to complete a new patient diary for IP and corticosteroid compliance. The patient will be instructed to return his/her treatment carton and diary at the following visit. The patient will be given back the treatment carton to be taken home. The patient will be reminded to record tinnitus presence and intensity in the SSNHL affected ear on a daily basis, and IP and corticosteroid intake. He will be asked to return the diary at the following visit, and to come in a fasting condition and not take the morning IP dose whenever the visit 4 is scheduled in the morning to allow a Pre-dose PK at Visit 4.

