### **11.1.4 Visit 4 (Day 14 ±2)**

The following tests and procedures will be performed:

- Checking for concomitant medication
- Inquiring about adverse event and fill an adverse event form if any
- The investigator or designee will check the IP and oral corticosteroids diary for compliance
- Checking the patient's diary for tinnitus
- Otologic examination and tympanometry

- Vital signs: blood pressure and heart rate, temperature
- 12-lead digitalised ECG
- Blood collection for routine hematology and serum chemistry (section 9.2.4)
- Serum sample for prestin and plasma sample for drug concentrations
- Audiometric tests: Pure tone audiometry and OAE tests (optional)
- Word and speech recognition Tests
- Pregnancy test (for WOCBP)

In case rescue medication is administered, please report in the e-CRF

The patient will be asked to complete specific questionnaires:

- Tinnitus and Vertigo Presence and Severity (NRS)
- QoL: EQ-5D-5L;
- TFI
- C-SSRS

The patient will be asked to complete a new patient diary for IP and corticosteroid compliance. The patient will be instructed to return his/her treatment carton and diary at the following visit,

The patient will be instructed to return all used and unused study treatment bottles at the following visit and to come in a fasting condition.

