### 6.14.2 Laboratory Data

Descriptive statistics of the observed values and change from baseline (continuous data) will be presented by treatment group and visit for each hematology, serum chemistry, and C-reactive protein parameter. For categorical laboratory parameters, subject counts within each category will be summarized. Shift tables from baseline to each post-baseline visit will also be presented, as applicable.

Each measurement (continuous data) will be classified as below, within, or above normal range, based on ranges supplied by the laboratory used. This study utilizes local laboratories only and therefore each local laboratory will provide its reference ranges. Shift tables in relation to the normal range from baseline to each follow-up visit will be presented.

Moreover, the number and percentage of subjects with treatment-emergent marked laboratory abnormalities will be tabulated for each laboratory parameter for which marked abnormalities are defined in the table below. For a given parameter, percentages will be based on the number of subjects at risk: those not meeting the criterion at baseline (or having a missing baseline value) and having at least one post-baseline value (including post-baseline value after last intake of study drug). The marked laboratory date abnormalities are defined as follows:

		Sponsor:	Sensorion
		Protocol Number:	SENS 401-201
STATISTICAL ANALYSIS PLAN. PHASE 2-3-4			

Category	Lab Test/ Examination Name	Unit	Marked Abnormalities				
			LL	LLL	HH	HHH	HHHH
CHEMISTRY	Alanine Aminotransferase	U/L			>3ULN	>5ULN	>8ULN
CHEMISTRY	Albumin	g/L	<30	<20			
CHEMISTRY	Alkaline Phosphatase	U/L			>2.5ULN	>5ULN	
CHEMISTRY	Aspartate Aminotransferase	U/L			>3ULN	>5ULN	>8ULN
CHEMISTRY	Bilirubin	umol/L			>2ULN	>5ULN	
CHEMISTRY	Calcium	mmol/L	<2.0	<1.75	>2.9	>3.1	
CHEMISTRY	Creatine Kinase	U/L			>5ULN	>10ULN	
CHEMISTRY	Creatinine	mmol/L			>1.5ULN or (>1.5baseline if baseline > ULN)	>3ULN or (>3baseline if baseline>ULN)	
CHEMISTRY	Creatinine Clearance	mL/min/ 1.73m 	<60	<30			
CHEMISTRY	Gamma Glutamyl Transferase	U/L			>2.5ULN	>5ULN	
CHEMISTRY	Glucose	mmol/L	<3.0	<2.2	>8.9	>13.9	
CHEMISTRY	Phosphate	mmol/L	<0.8	<0.6			
CHEMISTRY	Potassium	mmol/L	<3.2	<3.0	>5.5	>6.0	
CHEMISTRY	Sodium	mmol/L	<130		>150	>155	
CHEMISTRY	Triglycerides	mmol/L					
CHEMISTRY	Urate	umol/L			>590	>720	
CHEMISTRY	Urea	mmol/L			>2.5ULN	>5ULN	
HEMATOLOGY	Eosinophils	10  /L			>5.0		

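### Glucose: a possibly non-fasting baseline is compared with follow-up values meant to be fasting, which biases within-arm change downward and can drop new values above 8.9 mmol/L from one row of the marked-abnormality table

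*Protocol*

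**What the plan says.** **Sampling.** Protocol section 10.2.5 schedules the blood tests as follows: "A standard laboratory blood test will be performed at the screening visit (Visit1), on Day 14 (Visit 4), and End of treatment visit Day 28". The serum chemistry list contains "fasting glycaemia (fasting is not required at baseline", and the waiver is repeated on a separate line: "Glucose (no fasting is needed at screening". The same list ends with "creatine phosphokinase (CPK), triglycerides, cholesterol", which have no fasting rule of their own.

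At Visit 3 (Protocol 11.1.3) patients are asked "to come in a fasting condition and not take the morning IP dose whenever the visit 4 is scheduled in the morning". At Visit 4 (Protocol 11.1.4), for Visit 5: "The patient will be instructed to return all used and unused study treatment bottles at the following visit and to come in a fasting condition".

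**Analysis.** SAP section 6.2.2 defines the safety baseline as the last non-missing value up to the date of first dose, without regard to fasting state. SAP section 6.14.2 then plans three summaries that use it:
- "Descriptive statistics of the observed values and change from baseline (continuous data) will be presented by treatment group and visit";
- shift tables against the local normal range;
- treatment-emergent marked abnormalities, with percentages based on "those not meeting the criterion at baseline (or having a missing baseline value) and having at least one post-baseline value".

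The high limits for glucose are >8.9 mmol/L (HH) and >13.9 mmol/L (HHH), whatever the fasting state. The triglycerides row of that table is empty and cholesterol has no row.

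**The concern.** A change from baseline describes a patient only if both measurements were taken under the same conditions. Here the condition may differ systematically: food is allowed before the first sample and discouraged before the later ones. A fed baseline raises the reference value, so change is pulled down, some high-to-normal shifts may reflect only the meal, and patients are removed from the group in which new hyperglycaemia is counted.

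Glucose is a parameter that readers of this report will look at. Oral corticosteroids go to every patient without a contra-indication (Protocol 9.10.1), and exclusion criterion 11 allows them to be already under way at entry. Diabetes is not a named exclusion. Raised baseline values are therefore plausible, and the at-risk rule acts on exactly those patients.

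**Working it through.** The plan states no figure on this point, so there is nothing to reproduce. The first step is a reading of the text. The others are illustrations, and every glucose value in them is an assumption.

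**1. Which sample is the baseline?** By the flow chart and Protocol 10.2.5, the only laboratory draw scheduled before first dose is at screening. Under SAP 6.2.2 the glucose baseline is therefore in practice the screening sample, for which fasting is waived. Neither document provides for recording fasting status at a draw.

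**2. Bias in within-arm mean change.** Let *r* be the true fasting change, *f* the share of patients with a non-fasting baseline and *d* the mean non-fasting increment. Then

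apparent mean change = *r* − *f* × *d*

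and the bias is −*f* × *d*.

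| Assumed true change *r* (mmol/L) | *f* = 0.5, *d* = 0.5 | *f* = 1, *d* = 2 |
|---|---|---|
| 0 | 0 − 0.25 = −0.25 | 0 − 2.0 = −2.0 |
| 1.0 | 1.0 − 0.25 = +0.75 | 1.0 − 2.0 = −1.0 |
| 2.0 | 2.0 − 0.25 = +1.75 | 2.0 − 2.0 = 0 |

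The bias runs from −0.25 to −2.0 mmol/L. The sign of the observed change depends on *r*.

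**3. Patients leaving the HH row.** Take baseline glucose as normal with mean *m* and SD *s*. The share removed is P(baseline > 8.9) = 1 − Φ((8.9 − *m*)/*s*).
- *m* = 6, *s* = 1.5: (8.9 − 6)/1.5 = 1.93, share 2.7%, and 0.027 × 37 = 1.0 patient per Part 1 arm.
- *m* = 8, *s* = 2.5: (8.9 − 8)/2.5 = 0.36, share 35.9%, and 0.359 × 37 = 13.3 patients per arm.

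These counts include anyone whose fasting value would also have exceeded 8.9, so not every removal is an error.

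**4. New cases lost.** This was simulated with all baselines non-fasting. Underlying glucose had mean 5.5 and SD 1.0, with added visit variation of SD 0.5 at baseline and 1.0 afterwards. The true rise was 0.5 or 1.5. A new case is a patient whose fasting baseline would have been at or below 8.9 and whose fasting follow-up value is above it.
- Increment mean 1, SD 1: 19% to 29% of new cases are lost from the HH row.
- Increment mean 2, SD 1.5: 47% to 55% are lost.

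With only a share *f* sampled non-fasting, and that state unrelated to later glucose, these losses shrink in proportion.

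**5. A single patient.** A fed screening value of 9.2 and a fasting Day 14 value of 10 mmol/L: the patient met the HH criterion at baseline and is not at risk, and 10 is below 13.9. Neither high row counts this patient.

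**The case against.** The strongest defence is that the defect is confined to one descriptive parameter and that most of the information survives. Sampling rules are the same in blinded, randomised arms, and Protocol 13.5.4 plans no hypothesis testing for safety. SAP 6.14.2 already summarises observed values by arm and visit. All laboratory results are listed. Medically meaningful abnormalities are reported as adverse events (Protocol 12.4.1). Shift tables keep patients who were high at baseline. If the at-risk rule is applied limit by limit, a patient removed from HH can still count in HHH. All of this stands, and it limits the point to within-arm summaries and one table row.

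It also rules out several stronger readings that a reader might infer:
- *A fall in glucose is guaranteed.* Only a downward bias is built in, and a true rise can offset it. Nor is every high-to-normal shift an artefact: the corticosteroid course cited in Protocol 9.10.1 lasts 7 to 14 days and is then tapered, which could also lower glucose between visits.
- *The treatment comparison is biased.* The baseline sample precedes randomisation and its rule does not depend on arm, so the bias in mean change cancels in expectation.
- *Every follow-up sample is fasting.* Fasting is an instruction. At Visit 4 it may apply only to morning visits, and Protocol 10.2.5 gives none for early-termination samples.
- *Lipids share the whole problem.* The waiver names glucose only. With no lipid fasting rule, at most their change and shift tables are affected. No lipid limits are defined, so the at-risk problem cannot arise.

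What the defence does not answer is that the table meant to show emergent hyperglycaemia uses a baseline that may not be comparable, and nothing tells the reader so.

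**Conclusion.** The point holds for glucose, at modest weight. Followed as written, the plan puts a downward bias into within-arm glucose change and normal-range shifts, and leaves some new fasting values above 8.9 mmol/L uncounted in the HH row.

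The direction follows from the text, provided that some patients eat before screening and that most fast later as instructed. The size is unknown. The bias of 0.25 to 2.0 mmol/L, the 1 to 13 of 37 patients per arm, and the 19% to 55% of new cases lost all rest on assumed glucose values and show a range, not an estimate.

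No efficacy result, sample size or error rate is touched. The cost is reduced sensitivity for a glucose signal in a trial with near-universal corticosteroid use.

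**What to change.** Amend SAP section 6.14.2 as follows.
- Keep glucose change from baseline, because Protocol 13.5.4.2 requires it for each blood chemistry parameter, but label the baseline *fasting state not controlled* in the change and shift tables.
- Make observed Day 14 and Day 28 glucose by arm the main display.
- Beside the at-risk version of the glucose marked-abnormality table, add the number of all patients with any post-baseline value above each limit, cross-tabulated by baseline category: not above, above, missing.

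The cost is one extra table and a footnote. No new data are needed, so it also works for patients already sampled. The all-patient count will include hyperglycaemia present before treatment; the cross-tabulation shows it separately, which is why the at-risk table should be kept rather than replaced. Restricting the tables to fasting samples is not an alternative at present, because neither document provides for recording fasting status.

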#### **10.2.6 Adverse event collection**

Adverse events will be collected throughout the study and at every visit after consent. The medically-qualified investigator will be available to provide clinical judgment on all trial-related medical issues including adverse events and clinical laboratory values.

As a precautionary measure, specific attention will be paid to any potential serotonergic syndrome, particularly the following symptoms agitation, mental status changes (confusion, hypomania), myoclonus, shivering, tremor, hyperreflexia, ataxia, severe diarrhea or high fever will be checked carefully.

#### **10.2.7 Suicidality assessment:**

As per FDA guidelines for any neurologic investigational product, a suicidality assessment will be performed via the C-SSRS questionnaires (42) that will be completed at every visit from visit 2 until end of treatment visit (visit 5) by a trained personal. A series of questions about suicidal thoughts and behaviors will be asked. To most quickly and simply identify whether a person is at risk and needs assistance, a minimum of two and a maximum of six questions, depending on the answers will be asked. The patient should answer yes or no to the questions.

The C-SSRS questions use plain and direct language, which is most effective in eliciting honest and clear responses. This scale has been widely used in clinical trials and is translated in many languages. It has been validated by most of health authorities.

Results could trigger decisions about hospitalisation, counseling, referrals, and other actions. If any, an adverse event form should be completed.

### 10.3 Pharmacokinetic evaluation

Serum samples will be collected for pharmacokinetic (PK) analysis on Day 14 (Visit 4) and End of treatment visit (Visit 5): for more details, please refer to the laboratory manual. Ideally at least one V4 and V5 PK samples MUST be collected within 15 minutes of the 3rd ECG test being performed. Blood samples will be drawn, handled and stored in a secure location as per laboratory requirements, outlined in the laboratory manual which will be available at each investigational site, until shipment. The date and hour of the last drug intake and blood sampling will be recorded.

Several samples will be batched together in the same shipment. The person in charge of the shipment will be contacted by the CRO who will organize samples' shipment. If the site needs to transfer the samples rapidly (due to storage constraint for instance), the CRO should be contacted.

PK samples will be destroyed after the finalization of the complete Clinical Study Report. No further uses of biological samples are planned, i.e. for additional research.

### 10.4 Biomarker

Prestin has been described as a potential prognosis biomarker (40). Serum samples will be collected for prestin dosage at inclusion (Visit 2), or screening (Visit 1) in case the screening and inclusion visits are planned to be performed within 24hrs (to prevent an additional blood draw for a small blood volume), on Day 14 (Visit 4), and End of treatment visit (Visit 5). Blood samples will be drawn, handled and stored in a secure location as per laboratory requirements, outlined in the laboratory manual which will be available at each investigational site, until shipment. The date and hour of the last drug intake and blood sampling will be recorded.

## 11 STUDY PROCEDURES

### 11.1 Visits

Study procedures are described in the flow chart (Section 4). The following are general guidance relating to all visits.

Every attempt should be made to complete the follow-up visits during the defined window periods.

A final follow-up visit is required for all patients. In the rare cases the End of Study Visit (V6) cannot occur, any attempt to contact the patient should be recorded on a special contact form, until/unless appropriate information is obtained which will allow completion of final follow-up visit in the e-CRF, even after the anticipated timeframe.

Blood is collected by venipuncture. The exact time of sample collection should be transferred into database and should be collected on the laboratory request form for local blood sampling.

Important note: Any abnormal laboratory value, abnormal ECG parameter, SAE will be immediately rechecked for confirmation before making a decision of permanent discontinuation of IP for the concerned patient.

Patients will be advised to avoid skin exposure to strong sunlight and to wear sunglasses in bright sunlight for the duration of the study and for 1 week after the last dose.

#### 11.1.1 Screening visit - Visit 1 (Day-4 to Day 1)

Before any screening assessment is performed, complete and detailed information about the aim, the consequences and the constraints of the trial will be given by the investigator or a fully designated person, both verbally and by reviewing the information leaflet and consent form. If the subject agrees to perform the study, he will sign and date the Informed Consent form prior to any study-specific procedure. He will be given a copy of the information leaflet and consent form.

After obtaining consent, the investigator will connect to the e-CRF Portal, site secured by an SSL certificate to create the patient in the database data (patient attribution of code).

The following tests and procedures will be performed:

- Assessment of eligibility by review of inclusion and exclusion criteria
- Recording of the subject demography
- Complete Physical examination, including body weight and evaluation of main body systems/regions,
- Otologic examination and tympanometry
- Pure tone audiometry test unless performed within 24 hours prior to screening.
- Previous Medical, surgical and otologic history
- Concomitant medications (over the past 3 months)
- Recording of concomitant medication including oral corticosteroid use for SSNHL

- Vital signs: supine blood pressure and heart rate, temperature
- Blood collection for routine hematology, serum chemistry (section 9.2.4)
- Pregnancy test (for WOCBP)

If the patient meets all inclusion and no exclusion criteria (per history, exam and laboratory) the patient can be included in the study and will therefore be randomised.

### **11.1.2 Baseline visit - Visit 2 (Day 1)**

The following tests and procedures will be performed:

- Re-confirmation of eligibility by reviewing inclusion/exclusion criteria
- Checking for Concomitant medication
- Inquiring about adverse event and fill an adverse event form if any
- Recording of concomitant medication including oral corticosteroid use for SSNHL
- Vital signs: blood pressure and heart rate, temperature
- 12-lead digitalised ECG
- Otologic examination and tympanometry\*
- Audiometric tests: pure tone audiometry\*, OAE tests (optional)
- Word and speech recognition Tests
- Serum sample for Prestin concentration (before study drug intake)

The patient will be asked to complete specific questionnaires:

- Tinnitus and Vertigo presence and severity (NRS)
- QoL: EQ-5D-5L;
- TFI
- C-SSRS

\*Pure tone audiometry should be performed within the last 24 hours before the first study drug intake. In case of longer time or not performed at the study site, the Pure tone audiometry should be repeated. If a Pure tone audiometry was performed at the study site for screening less than 24 hours before the first study drug intake, there is no need to repeat it.

After all assessments have been completed, the investigator will connect to the IWRS for allocation of a randomised treatment kit number. The investigator will dispense to the subject the corresponding study drug that is to be taken at the site, immediately after all baseline assessments are performed. Patient should be instructed to take 3 tablets (one from each bottle of one clinical pack). Date and time of the intake should be recorded on the patient diary and e-CRF.

The patient will be given the treatment carton to be taken home and asked to complete a patient diary for IP and corticosteroid compliance. The patient will be instructed to return his/her treatment carton and diary at the following visit.

---

The patient will also be asked to record tinnitus presence and intensity in the SSNHL affected ear on a daily basis in the patient diary. He will be asked to return the diary at the following visit.

